7.2 Adverse events

Unless noted otherwise, the AE summary tables will include TEAEs occurring during the extension study i.e., AEs that started or worsened on or after double-blind study treatment start date of the extension study up to 30 days after double-blind study treatment end date. An AE that started or worsened during any unplanned double-blind study treatment interruption (e.g., due to AE) will be considered as treatment-emergent. In addition, an AE that started or worsened during a planned double-blind study treatment interruption (i.e., the run-out period or safety follow-up period) that falls in the treatment-emergent time window defined above, will be considered as treatment-emergent.

AEs will be coded using MedDRA. The MedDRA version used for reporting will be specified in the footnote of the applicable output.

The number and percentage of subjects experiencing a TEAE occurring during the extension study (including SAEs, AESIs after adjudication by the ISB, and AEs leading to premature discontinuation or temporary interruption of double-blind study treatment) will be summarized by SOC and/or PT, and/or maximum intensity.

Each AESI category (i.e., excessive daytime sleepiness, cataplexy, complex sleep behavior including hallucinations/sleep paralysis, suicide/self-injury, narcolepsy-like symptoms) will be summarized by PT separately.

A subject with multiple intensities reported for an AE will be summarized under the maximum intensity recorded for the event.

Apart from the summaries of occurrences, where each event is counted, a subject with multiple occurrences of an AE is counted only once in the AE category (e.g., SOC, PT). If a single AE worsens on the same treatment group, then this event will be considered as one occurrence.

AEs will be sorted by descending frequency, first in the ACT-541468 50 mg dose level, then in the ACT-541468 25 mg dose level, then in the ACT-541468 10 mg, then in the placebo treatment group, and finally in the ex-placebo/ACT-541468 25 mg. After this ordering, SOCs are presented in alphabetical order with PT sorted within SOC in alphabetical order.

The following AE summary tables will be provided:

- TEAEs,
- TEAEs during the double-blind study period^a,
- TEAEs occurring (i.e., that started or worsened) during the treatment withdrawal period (based on the TWS),
- TEAEs during the double-blind study period^a related to study treatment as assessed by the investigator and/or sponsor,
- AEs leading to premature discontinuation of double-blind study treatment,
- AEs leading to temporary interruption of double-blind study treatment,
- Treatment emergent SAEs (including occurrences),
- Treatment emergent SAEs related to study treatment (including occurrences),
- Most frequent (threshold to be defined at time of reporting) non-serious TEAEs (including occurrences),
- Treatment emergent AESIs after ISB adjudication,
- TEAEs during the double-blind study period^a related to abuse (as defined in the document *Search specifications for safety monitoring*),

- TEAEs during the double-blind study period^a based on selected Standardized MedDRA Queries or pre-defined search criteria (as defined in the document *Search specifications for safety monitoring*),
- TEAEs with fatal outcome,
- Total number of deaths (those occurring on or after double-blind study treatment start date of the extension study up to 30 days after double-blind study treatment end date).

^a Includes only those TEAEs occurring (i.e., that started or worsened) during the double-blind study period [see Section 12.2].

All AEs will be listed including AEs recorded as ongoing at the start of double-blind study treatment.

An AE listing will be provided also for subjects who were not randomized and subjects who were randomized but did not take double-blind study treatment. Subjects who were not randomized due to an AE or discontinued the study due to an AE will be reported in that listing. In addition, a separate listing will be provided for deaths with cause of death using the ENR Set.

AEs submitted for adjudication will be listed flagging separately: AEs that were adjudicated as an AESI and AEs that were considered an AESI as per the investigator's judgment.

The number of subjects (including occurrences) with at least one case submitted for ISB adjudication will be summarized and listed.

An incomplete (day or month missing) or missing AE date will be imputed as described in Table 3. The 'lower limit' and 'upper limit' refer to the earliest and latest possible dates, respectively. As an example: if AE onset date is MAR2017 (day missing), the lower limit is 01MAR2017 and the upper limit is 31MAR2017; if AE onset date is 2017 (day and month missing), the lower limit is 01JAN2017 and the upper limit is 31DEC2017.

Table 3 Imputation rules for an incomplete or missing AE date

Field	Incomplete date	Missing date
AE resolution date	The upper limit.	No imputation; the AE is considered as ongoing.
AE onset date	
The rules below apply in the order presented:
 
 1. For AEs reported as ongoing from the confirmatory study, the lower limit is used. 2. If the (imputed) AE end date is on or after the start of double-blind study treatment, and if the double-blind study treatment start falls within the upper and lower limits (inclusive), the double-blind study treatment start date is used. 3. If the AE resolution date is missing, and if the double-blind study treatment start falls within the upper and lower limits (inclusive), the double-blind study treatment start date is used. 4. In all the other cases, the lower limit is used. 	Whichever is the earlier of the AE resolution date or double-blind study treatment start date*.

AE = adverse event.

*If an AE is reported as ongoing (from confirmatory study) and if the onset date is missing then the double-blind study start date of the confirmatory study should be used.

The purpose of imputing AE dates is only to assign an AE to a specific treatment phase for the summary tables and listings. However, only the actual dates as reported in the eCRF will be listed. No imputed date is considered in the medical evaluation of an AE.

7.3 Laboratory tests

Laboratory analyses are based on data received from the central laboratory. Laboratory data will be converted into SI units. Unless noted otherwise, summaries and listings will include scheduled, re-test and unscheduled assessments.

Descriptive summary statistics for each scheduled visit (re-test excluded) will be provided for observed values and change from baseline (baseline as defined in Section 11.4) in both hematology and blood chemistry laboratory parameters.

The change from baseline to the last value (re-test and unscheduled assessments excluded) in the double-blind study period for hematology and blood chemistry parameters will be summarized.

Marked laboratory abnormalities are defined in Table 4. The number and percentage of subjects with marked laboratory abnormalities during double-blind study treatment will be tabulated. In the event of multiple occurrences, a subject will be counted only once but may be reported in more than one marked laboratory abnormality criterion of a given parameter.

Percentages will be based on the number of subjects at risk, i.e., those having at least one post-baseline value for a given parameter.

Shift from baseline to worst value post-baseline based on laboratory normal ranges will be provided for the following laboratory parameters:

- Liver enzymes: ALT, AST, gamma-glutamyl transpeptidase and TBIL.
- Thyroid hormones: thyroid-stimulating hormone, free triiodothyronine and free thyroxine.
- Lipids: total cholesterol and triglycerides.
- Hematology: leucocytes, neutrophils, lymphocytes, and eosinophils.

All laboratory data for subjects with at least one marked laboratory abnormality during double-blind study treatment will be listed. Any local laboratory data collected will be listed separately.

Table 4 **Marked abnormalities in laboratory parameters for reporting**

Laboratory parameter	Criteria for marked laboratory abnormalities
Hematology (SI unit)	
Hemoglobin (g/L)	< 100 < 80 > 20 above ULN or > 20 above baseline if baseline > ULN > 40 above ULN or > 40 above baseline if baseline > ULN
Hematocrit (%)	< 32% (Male); < 28% (Female) < 20% > 60% (Male); > 55% (Female)

Laboratory parameter	Criteria for marked laboratory abnormalities
	> 65%
Platelets (10 ⁹ /L)	< 75 < 50 > 600 > 999
Leucocytes (10 ⁹ /L)	< 3.0 < 2.0 > 20.0 > 100.0
Neutrophils (10 ⁹ /L)	< 1.5 < 1.0
Eosinophils (10 ⁹ /L)	> 5.0
Eosinophils (%)	> 5%
Lymphocytes (10 ⁹ /L)	< 0.8 < 0.5 > 4.0 > 20.0
Reticulocyte (%)	> 2.5%
Blood chemistry (SI unit)	
ALT (U/L)	> 3 × ULN > 5 × ULN > 10 × ULN
AST (U/L)	> 3 × ULN > 5 × ULN > 10 × ULN
ALP (U/L)	> 2.5 × ULN > 5 × ULN
Total bilirubin (µmol/L)	> 2 × ULN > 5 × ULN
Creatinine (µmol/L)	> 1.5 × ULN or > 1.5 × baseline if baseline > ULN > 3 × ULN or > 3 × baseline if baseline > ULN

Laboratory parameter	Criteria for marked laboratory abnormalities
Creatinine clearance (ml/min/1.73 m ²)	< 30 < 60
Albumin (g/L)	< 30 < 20
Calcium (mmol/L)	< 2.0 < 1.75 > 2.9 > 3.1
Potassium (mmol/L)	< 3.2 < 3.0 > 5.5 > 6.0
Sodium (mmol/L)	< 130 > 150 > 155
Chloride (mmol/L)	< 74 > 131
Creatine kinase (µg/L)	> 5 × ULN > 10 × ULN
Gamma-glutamyl transferase (U/L)	> 2.5 × ULN > 5 × ULN
Blood urea nitrogen (mmol/L)	> 2.5 × ULN > 5 × ULN
Uric acid (µmol/L)	> 590 > 720
Glucose (mmol/L)	< 3 < 2.2 > 8.9 > 13.9
TSH (mIU/L)	< 0.28 > 6.6
Free T ₃ (pmol/L)	< 2.8 > 7.8
Total T ₃ (nmol/L)	< 0.9

Laboratory parameter	Criteria for marked laboratory abnormalities
	> 3.6
Free T ₄ (pmol/L)	< 7.2 > 24
Total T ₄ (nmol/L)	< 53 > 210
Triglycerides	> 5.7 mmol/L
Total cholesterol	> 2 × ULN

ALP = alkaline phosphatase; ALT = alanine aminotransferase; AST = aspartate aminotransferase; SI unit = International System of Units; TSH = thyroid-stimulating hormone; T₃ = triiodothyronine; T₄ = thyroxine; ULN = upper limit of normal.

Elevated liver parameters during double-blind study treatment will be summarized: the number and percentage of subjects meeting the criteria defined below within a given central laboratory sample will be tabulated by treatment group. Percentages will be based on the number of subjects at risk, i.e., those having at least one post-baseline value for all parameters within the given criteria.

- AST or ALT > 3 × ULN.
- AST or ALT > 5 × ULN.
- AST or ALT > 10 × ULN.
- TBIL > 1.5 × ULN and > 2 × ULN.
- ALP > 1.5 × ULN.
- (ALT or AST > 3 × ULN) and (TBIL > 1.5 × ULN).
- (ALT or AST > 3 × ULN) and (TBIL > 2 × ULN).

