7.4 Electrocardiography

Unless noted otherwise, ECG summaries and listings will include scheduled, re-test and unscheduled assessments.

Descriptive summary statistics for each scheduled visit (re-test excluded) will be provided for observed values and change from baseline (baseline as defined in Section 11.4) to Visit 3 (Week 14), Visit 4 (Week 27), Visit 5 (Week 40) and Visit 6 (Week 41) in ECG parameters (QT corrected according to Fridericia's formula, QT corrected according to Bazett's formula, heart rate, PR, and QRS).

Marked ECG abnormalities are defined in Table 5. The following summaries will be provided for each ECG parameter:

- Number and percentage of subjects having a marked ECG abnormality during the double-blind study period,
- Number and percentage of subjects having a marked ECG abnormality during the treatment withdrawal period (based on the TWS).

For the summaries above, percentages will be based on the number of subjects at risk: those having at least one post-baseline value in the study period under consideration per ECG parameter for criteria based on post-baseline values only, or those having a baseline value and at least one post-baseline value in the study period under consideration per ECG parameter for criteria based on change from baseline. For non-mutually exclusive criteria (i.e., HR < 45 bpm and < 50 bpm), a subject will be counted only once in the event of multiple occurrences but may be reported in more than one marked ECG abnormality criterion of a given parameter. For mutually exclusive criteria (e.g., HR and QTc), only the subject's worst post-baseline value (or worst change from baseline value) will be counted.

ECG findings during the double-blind study period and during the treatment withdrawal period (based on the TWS) will be summarized separately and listed.

ECG abnormality categories and findings will be sorted by descending frequency, first in the ACT-541468 50 mg dose level, then in the ACT-541468 25 mg dose level, then in the ACT-541468 10 mg, then in the placebo treatment group, and finally in the ex-placebo/ACT-541468 25 mg. After this sorting, ECG abnormality categories will be presented in alphabetical order with ECG finding sorted within ECG abnormality category in alphabetical order.

All ECG values for subjects with at least one marked ECG abnormality during double-blind study period or during the treatment withdrawal period will be listed.

Table 5 **Marked abnormalities in ECG parameters**

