11.4 Baseline

Unless otherwise defined in the specific analysis section, baseline is defined as follows:

1. For subjects entering ID-078A303 and assigned to the same treatment arm as that of the confirmatory studies (ACT-541468 10 mg, 25 mg, or 50 mg, or placebo), baseline is the last non-missing assessment performed or value measured before or on the day of first dose of double-blind study treatment in the confirmatory study.
2. For subjects entering ID-078A303 who received placebo in the confirmatory studies and who are randomized (switched) to 25 mg of ACT-541468 in the extension study, baseline is the last non-missing assessment performed or value measured before or on the day of first dose of double-blind study treatment in the extension study. This could be either data collected at Visit 1 of the extension study or collected in the confirmatory study. An assessment taken on the day of the double-blind study treatment start date is considered a baseline assessment and is not considered a post-baseline assessment in the double-blind study period.

Subjects with no data on a particular parameter before the first treatment administration will have a missing baseline (and change from baseline) for this parameter.

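### SAP 7.3 counts laboratory abnormalities on double-blind treatment over a denominator with no period limit, and plans no new-onset count for its fixed cut-offs

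*SAP*

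**What the plan says.** **Numerator.** SAP 7.3 says of the Table 4 criteria: "The number and percentage of subjects with marked laboratory abnormalities during double-blind study treatment will be tabulated". The elevated-liver table in the same section is also limited to double-blind treatment.

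**Denominator.** "Percentages will be based on the number of subjects at risk, i.e., those having at least one post-baseline value for a given parameter". The liver table uses the same construction, asking for a post-baseline value on every parameter in the criterion. Neither names a study period or refers to status at baseline.

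**Baseline and post-baseline.** For subjects who stay on their confirmatory-study arm, SAP 11.4 sets baseline at the last non-missing assessment or "value measured before or on the day of first dose of double-blind study treatment in the confirmatory study". For subjects switched from placebo to 25 mg it runs to the day of the first extension dose. SAP 11.5 treats any later assessment up to end of study as post-baseline.

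**Criteria.** Most Table 4 cut-offs are fixed numbers or multiples of the ULN. Two parameters refer to the subject's own baseline: high hemoglobin ("> 20 above ULN or > 20 above baseline if baseline > ULN") and creatinine ("> 1.5 × ULN or > 1.5 × baseline if baseline > ULN"), each with a second, more severe tier built the same way.

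**ECG comparison.** SAP 7.4 ties the denominator to the period, "those having at least one post-baseline value in the study period under consideration per ECG parameter for criteria based on post-baseline values only", and for change criteria uses "those having a baseline value and at least one post-baseline value in the study period under consideration per ECG parameter for criteria based on change".

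**The concern.** There are two separate points.

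1. **The denominator is wider than the numerator.** A subject with no laboratory value on extension treatment cannot contribute an event, yet can be counted as at risk. This pulls the percentage down. One route, a Visit 1 sample taken before the first extension dose, is open only to the continuing groups, because in the ex-placebo group that sample is the baseline. The columns therefore do not share one definition of at risk.

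2. **Presence is not onset.** With a fixed cut-off, a subject whose creatinine clearance is 55 before any drug and 55 at every visit is tabulated under the below-60 criterion. The primary objective (SAP 3.1) is long-term safety, and a reader will want to know how many subjects crossed the cut-off on treatment. The shift tables do not cover creatinine clearance, glucose, electrolytes, hemoglobin or creatine kinase.

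**Working it through.** The plan states no rate or sample size for these tables, so there is no figure to reproduce. The check compares the definitions and then sizes the effects under stated assumptions.

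**Who can enter the denominator without a value on treatment**

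| Only extension value available | Continuing groups | Ex-placebo group |
|---|---|---|
| Visit 1, before first extension dose | post-baseline: counted | baseline: not counted |
| Run-out period | post-baseline: counted | post-baseline: counted |
| More than 7 days after last intake, early stopper | excluded (SAP 7.1) | excluded (SAP 7.1) |

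SAP 11.4 says that a sample on the treatment start date is not post-baseline in the double-blind period. That sentence stands under the ex-placebo rule, and the 7.3 denominator names no period, so it does not clearly close the first row. SAP 11.2 starts the double-blind period on the day of first dose, so a period limit alone would not exclude a same-day pre-dose sample either. The laboratory visit schedule is not in the documents at hand, so how often each row occurs is unknown. The COVID-19 addendum (Section 2.2) makes missing on-treatment central samples more likely, because it replaces clinic visits with calls and discourages local laboratory tests.

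**Size of the denominator effect.** Let p be the true percentage among subjects with a double-blind value, and f the share of counted subjects without one (assumed). Tabulated percentage = p × (1 − f). With p = 3.00%:

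- f = 1%: 2.97%
- f = 5%: 2.85%
- f = 10%: 2.70%

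**Size of the presence-versus-onset effect.** Let b be the share past the cut-off at baseline, k the probability that such a subject is still past it on treatment, and i the new-onset risk in the others (all assumed). Tabulated percentage = b·k + (1 − b)·i. With i = 1% and k from 0.5 to 0.9:

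| b | Tabulated | Share of counted cases that are pre-existing |
|---|---|---|
| 0.5% | 1.25–1.45% | 20–31% |
| 2% | 1.98–2.78% | 51–65% |
| 5% | 3.45–5.45% | 72–83% |
| 10% | 5.90–9.90% | 85–91% |

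**Effect on the comparison.** With equal b and k in both groups, the b·k term cancels and the difference is (1 − b)·(i₁ − i₀). For i = 3% versus 1% and k = 0.7:

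| b | Active | Placebo | Difference (points) | Ratio |
|---|---|---|---|---|
| 0% | 3.00% | 1.00% | 2.00 | 3.00 |
| 2% | 4.34% | 2.38% | 1.96 | 1.82 |
| 5% | 6.35% | 4.45% | 1.90 | 1.43 |
| 10% | 9.70% | 7.90% | 1.80 | 1.23 |

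The ratio shrinks, while the difference is nearly kept. This depends on equal b. Take new onset of 2% versus 1% and k = 0.7:

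- b = 8% in both groups: 0.056 + 0.92 × 0.02 = 7.44% versus 0.056 + 0.92 × 0.01 = 6.52%, a difference of 0.92 points.
- b = 6% active and 8% placebo: 0.042 + 0.94 × 0.02 = 6.08% versus 6.52%, so the direction reverses.

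**The case against.** **The period is implied.** The laboratory section has a single marked-abnormality table, limited to double-blind treatment, and the denominator sentence follows soon after. ECG has two such tables and so must name the period. SAP 1 reports extension data only, which keeps confirmatory-study values out, and SAP 7.1 removes late values after early discontinuation. This narrows the gap to the Visit 1 and run-out routes but does not close them, because 11.5 defines post-baseline up to end of study.

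**Presence on treatment is a legitimate count.** Section 7.3 does not claim to report new onset. Section 7.4 likewise keeps subjects who were abnormal at baseline for its fixed cut-offs (for example PR > 200 ms). This stands, and it is why the present table should not be called wrong.

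**Other outputs carry baseline information.** Section 7.3 plans change-from-baseline summaries for hematology and chemistry, shift tables for 13 parameters (TSH among them), and a listing of all laboratory data for each affected subject. A reader might infer that nothing separates old from new abnormalities; these outputs contradict that. What remains is that the shifts use normal ranges rather than Table 4 cut-offs, omit the parameters named above, and would leave new onset to be counted by hand from listings.

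**Excluding baseline cases has a cost.** A subject falling from a clearance of 59 to 31 would leave the below-60 count and never reach below 30. Glucose rising from 9.0 to 13.5 would vanish in the same way between the cut-offs of 8.9 and 13.9. This stands, and it argues for adding a count rather than substituting one.

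**Conclusion.** The point holds in a limited form. The denominator in 7.3, for both the Table 4 and liver tables, is not tied to the period of its numerator and is not built alike for the continuing and ex-placebo columns. The bias is downward and small: at most a 10% relative reduction if 10% of counted subjects lack a double-blind value, and 1% if 1% do.

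For fixed cut-offs the table measures presence, and pre-existing cases could be a large part of it: 72–83% of those counted at 5% baseline prevalence and 1% new onset. All of these rates are assumptions; the documents give none.

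A reader might infer that the table fails as a safety measure or hides real differences between groups. The documents do not support that. The output is descriptive, with no ratio or test planned for laboratory data, and the risk difference is little changed when baseline prevalence is similar. Similar prevalence is plausible because the continuing arms stem from the confirmatory-study assignment. It is not assured, since entrants are willing completers and the active groups are not re-randomised. A reader might also take every criterion to ignore baseline, but high hemoglobin and creatinine move to a baseline-relative cut-off when baseline exceeds the ULN.

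**What to change.** In SAP 7.3, for both the Table 4 and elevated-liver tables:

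1. Define at risk as having at least one value (for the liver table, on every parameter in the criterion) after the first extension dose and within the double-blind study period of 11.2, including the 7-day allowance in 7.1 for early stoppers.
2. For the high-hemoglobin and creatinine criteria, also require a baseline value, as 7.4 does for ECG change criteria.
3. Keep the all-occurrence table. Add a column or companion table counting subjects who did not meet the criterion at baseline, with those subjects as its denominator and a footnote on how a missing baseline is handled.

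The cost is a few sentences, a baseline-status flag in the analysis dataset and one extra table; no new data are needed. Denominators will vary slightly by criterion. The new-onset count will still refer to different baselines in the continuing and ex-placebo columns (SAP 11.4), which a footnote should state.

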7.4 Electrocardiography

Unless noted otherwise, ECG summaries and listings will include scheduled, re-test and unscheduled assessments.

Descriptive summary statistics for each scheduled visit (re-test excluded) will be provided for observed values and change from baseline (baseline as defined in Section 11.4) to Visit 3 (Week 14), Visit 4 (Week 27), Visit 5 (Week 40) and Visit 6 (Week 41) in ECG parameters (QT corrected according to Fridericia's formula, QT corrected according to Bazett's formula, heart rate, PR, and QRS).

Marked ECG abnormalities are defined in Table 5. The following summaries will be provided for each ECG parameter:

- Number and percentage of subjects having a marked ECG abnormality during the double-blind study period,
- Number and percentage of subjects having a marked ECG abnormality during the treatment withdrawal period (based on the TWS).

For the summaries above, percentages will be based on the number of subjects at risk: those having at least one post-baseline value in the study period under consideration per ECG parameter for criteria based on post-baseline values only, or those having a baseline value and at least one post-baseline value in the study period under consideration per ECG parameter for criteria based on change from baseline. For non-mutually exclusive criteria (i.e., HR < 45 bpm and < 50 bpm), a subject will be counted only once in the event of multiple occurrences but may be reported in more than one marked ECG abnormality criterion of a given parameter. For mutually exclusive criteria (e.g., HR and QTc), only the subject's worst post-baseline value (or worst change from baseline value) will be counted.

ECG findings during the double-blind study period and during the treatment withdrawal period (based on the TWS) will be summarized separately and listed.

ECG abnormality categories and findings will be sorted by descending frequency, first in the ACT-541468 50 mg dose level, then in the ACT-541468 25 mg dose level, then in the ACT-541468 10 mg, then in the placebo treatment group, and finally in the ex-placebo/ACT-541468 25 mg. After this sorting, ECG abnormality categories will be presented in alphabetical order with ECG finding sorted within ECG abnormality category in alphabetical order.

All ECG values for subjects with at least one marked ECG abnormality during double-blind study period or during the treatment withdrawal period will be listed.

Table 5 **Marked abnormalities in ECG parameters**

ECG parameter	Criteria for marked ECG abnormalities
QTcF, QTcB (ms)	> 450 and ≤ 480 > 480 and ≤ 500 > 500 > 30 and ≤ 60 increase from baseline > 60 increase from baseline
HR (bpm)	< 45 < 50 > 10 and ≤ 20 decrease from baseline > 20 decrease from baseline
PR (ms)	> 200
QRS (ms)	> 110

bpm = beats per minute; ECG = electrocardiogram; HR = heart rate; QTcB = QT corrected according to Bazett's formula; QTcF = QT according to Fridericia's formula.

